Study: # 7764 entitled An Open-Label Pilot Study of Sublocade as Treatment for Opiate Use Disorder

PI: [name]
NCT# NCT03861338
Data Analysis Plan created 2-25-2019

C. DATA MANAGEMENT AND ANALYSIS

C1. Data Acquisition and Transmission

All data will be obtained specifically for research purposes. Data will be entered into an Excel spreadsheet coded with a unique identifier assigned to each participant. Departmental, HIPAA-compliant Research Subject Registration System, will however contain participants' names.

C2. Data Entry Methods

As noted above, data will be entered into an Excel spreadsheet. Data management will include: 1) protocol management; 2) patient scheduling; 3) regulatory reporting and 4) management of research organizations, personnel, and collaborators. The research staff will collect and input data on a daily, basis to reduce the likelihood of errors. Information collection and analysis and study-specific data collection will be easily retrievable, organized, and reviewed on an ongoing basis as well.

C3. Data Analysis Plan

Overview of Data Analytic Plan

Sample size: A total of 10 participants will be recruited.

A total of 10 patients will be recruited over a 6-month period. The main analyses in this study will be on the intent-to-treat (ITT) sample, i.e. on all enrolled patients who receive study medication, and all tests will be two-sided, performed at significance $\alpha=0.05$, except where noted. Before specific statistical techniques are applied in order to test the hypotheses of interest, we will examine all variables at all time points for outliers. The distributions of all continuous variables will be checked for normality, and transformations will be employed, if necessary, before applying specific parametric techniques.

Hypotheses testing:

Primary Outcome: The proportion of participants successfully inducted onto BXR.

Secondary Outcomes: BXR treatment will be associated with decreased opioid use for OUD patients positive for HPSO. The primary outcome measure will be opioid use during the last two weeks of the study compared to baseline as measured by a combination of urine toxicology and self-report. BXR injection will be associated with reduce symptoms of craving and symptoms of withdrawal as compared to baseline.

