Study Days 1-3: Buprenorphine induction: Study procedures will begin with all participants being inducted onto BSL. For buprenorphine to be safely administered, participants must be in withdrawal from opioids. Individuals will be instructed to abstain from opioids starting at consent and begin buprenorphine medication the day after consent. The day after consent, patients will return to the STARS clinic and be administered a Clinical Opiate Withdrawal Scale (COWS). If found to be in mild withdrawal (COWS score > 6), participants will be started on buprenorphine 2 mg followed by further doses of buprenorphine up to 8 mg on day 1. Because HPSO use may lead to a delayed onset of opioid withdrawal syndrome, the first day that buprenorphine is administered may not be up to three days after a participant's last opioid use.

Whichever day the first dose of BSL is administered will be considered the first day of the induction. The buprenorphine dose will be advanced to a target dose of 24 mg per day on a fixed-flexible schedule, with stabilization at a lower dose if the patient does not tolerate side effects at higher doses. Adequate dosing of buprenorphine is important to its effectiveness, and 16 mg to 24 mg per day is considered the target according to most guidelines.

COMFORT MEDICATIONS: Participants will be given comfort medications to help manage their withdrawal for the first two weeks of the treatment study as needed. Comfort medications prescribed will be

clonidine, clonazepam, prochlorperazine, and zolpidem. Participants will be told that medications may cause some side effects such as sleepiness, lowered blood pressure (which may produce dizziness or a tendency to feel faint), or upset stomach. Participants will be instructed that they should use caution when driving a vehicle or operating appliances or machinery during this time.

Study Day 4: Participants will receive BXR under open-label conditions.

Maintenance Buprenorphine Dosing with BXR treatment: After successful induction onto sublingual buprenorphine, participants will receive BXR (Sublocade) 300 mg subcutaneous injection as per FDA—approved prescribing instructions. The second injection of Sublocade 300 mg will be administered 28 days later. The third injection will occur 28 days subsequent to the second injection at a dose of 100 mg.

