Quality of Life: The Quality of Life Enjoyment and Satisfaction Questionnaire- Short Form (QLES-Q-SF): is a 16-item self-report questionnaire, assessing the degree of enjoyment and satisfaction experienced by subjects in different areas of daily functioning based on a 5-point scale. It will be collected at baseline and weekly thereafter (Endicott et al. 1993).

Assessment of Side Effects and Medication Compliance

Systemic Assessment for Treatment Emergent Events (SAFTEE): The psychiatrist or research nurse queries the patient and logs side effects and other treatment emergent events since the past visit, recording severity, action taken, and whether the side effect(s) is continuing or resolved.

Assessing Medication Compliance: (1) The study psychiatrist during each weekly evaluation queries and records patients' self-reported compliance and missed doses. (2) Compliance is also monitored with pill counts conducted by the research nurse.

NIDA/VA Serious Adverse Event Form and NIDA Serious Adverse Event Tracking and Reporting System (SAETRS, on line): Whenever a serious adverse event occurs the event is described and reported IRB and to the NIDA project officer. SAETRS is a web-based application that helps collect, track, store, analyze and report serious adverse events (SAETRS).

Please see table of study assessments for complete detail of assessments.

Please attach copies, unless standard instruments are used
study assessments 1.24.19.pdf

Off label and investigational use of drugs/devices

Choose from the following that will be applicable to your study

Drug

Select the number of drugs used in this study

1

Drug #1

Name of the drug

sublocade

Manufacturer and other information

Other name: Buprenophine extended-release

Manufacturer: Indivior

Approval Status

No IND is required

Choose one of the following options

FDA has determined that IND is not required

Research Related Delay to Treatment

Will research procedures result in a delay to treatment?

Yes

Maximum duration of delay to any treatment

Active treatment of known efficacy (detoxification) begins when patients have signed study consent and begin outpatient detoxification at STARS. A delay of up to 2 weeks is possible prior to enrollment.

Maximum duration of delay to standard care or treatment of known efficacy

Up to two weeks.

Treatment to be provided at the end of the study

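### Applied to the proportion inducted onto BXR, the SAP's dosed-only analysis set can overstate that proportion or leave it unchanged, but never lower it

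*SAP*

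**What the plan says.** SAP C3 defines one analysis set. The main analyses are to be done "on all enrolled patients who receive study medication", and the SAP calls this the intent-to-treat sample. Under Hypotheses testing it then lists "Primary Outcome: The proportion of participants successfully inducted onto BXR". No separate denominator is given, and neither successful induction nor study medication is defined. On numbers, the SAP says only that "A total of 10 participants will be recruited".

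The order of events is in the protocol, under Medication and rationale:

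- Consent comes first: "Individuals will be instructed to abstain from opioids starting at consent and begin buprenorphine medication the day after consent".
- The first BSL dose has a condition: "For buprenorphine to be safely administered, participants must be in withdrawal from opioids". The threshold is a COWS score above 6.
- The injection comes last: "After successful induction onto sublingual buprenorphine, participants will receive BXR", planned for Study Day 4.

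**The concern.** Receiving study medication is a step on the way to the outcome being counted. Someone who consents and never takes a first BSL dose has not been inducted onto BXR, yet falls outside the set. If the set supplies the denominator, that failure disappears from the result.

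Aim 1 of the protocol is feasibility, and the protocol says that promising results would support a controlled trial. A proportion inducted is a direct measure of feasibility, and with about 10 people each one removed from the denominator shifts it visibly. As written, two analysts with the same data could report different values, and the stated set can err in one direction only.

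**Working it through.** **The plan's own figure.** There is none to reproduce for this outcome. The documents give no expected induction rate, precision target, threshold or rate of loss before dosing. The only number is the planned 10.

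**Direction.** Let I be the number inducted onto BXR, m the number who receive any study medication (BSL or BXR), and n the number who consent. BXR follows BSL, so everyone counted in I is also counted in m:

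I ≤ m ≤ n, hence I/m ≥ I/n.

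The two are equal when m = n (nobody lost before the first dose) or I = 0. No other assumption is needed.

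**Size, by assumed example.** Take n = 10 consented and let k be the number lost before the first BSL dose. The values of I and k are assumptions; the documents give neither.

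- All-consented estimate: I/10.
- Dosed-set estimate: I/(10 − k).
- Difference: I/(10 − k) − I/10 = I·k/[10(10 − k)]. This is 0 for k = 0, I/90 for k = 1 and I/40 for k = 2.

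Intervals are Clopper-Pearson 95%.

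| I | All consented (also k = 0) | k = 1 | k = 2 |
|---|---|---|---|
| 5 | 50.0% (18.7–81.3) | 55.6%, +5.6 points | 62.5%, +12.5 points |
| 6 | 60.0% (26.2–87.8) | 66.7%, +6.7 points | 75.0%, +15.0 points |
| 7 | 70.0% (34.8–93.3) | 77.8%, +7.8 points | 87.5%, +17.5 points |
| 8 | 80.0% (44.4–97.5) | 88.9%, +8.9 points | 8/8 = 100%, +20.0 points |
| 9 | 90.0% (55.5–99.7) | 9/9 = 100%, +10.0 points | not possible |

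For I = 7 the dosed-set intervals are 40.0–97.2% (k = 1) and 47.3–99.7% (k = 2).

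Most of the shifted estimates stay inside the wide all-consented interval. Two do not: 8 inducted with two losses, and 9 inducted with one loss. Both give 100%, above the all-consented upper limits of 97.5% and 99.7%.

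**Can such losses occur?** The first dose is planned for the day after consent, so there is a gap in which someone may not return. Failing to reach the withdrawal threshold on that day is a weaker route. The protocol recognises that withdrawal may be delayed after high-potency opioid use. In a sentence that is garbled but evidently allows up to three days from last use, it lets the first dose come later, and it counts the induction from whichever day that dose is given. The main route is therefore people who consent and never start.

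**The case against.** Four points can be made for the plan.

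1. *The set may not govern this outcome.* The sentence defining it goes on to two-sided tests, and no test is stated for the induction proportion. The outcome speaks of participants, the same word the SAP uses for the 10 recruited. On that reading nobody is dropped. This stands as a possible reading, but the SAP does not state it, and the only analysis set it does state points the other way.

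2. *Enrolment may coincide with the start of treatment.* Under Research Related Delay to Treatment, active treatment "begins when patients have signed study consent and begin outpatient detoxification at STARS", and "A delay of up to 2 weeks is possible prior to enrollment". Elsewhere the protocol describes a delay of the same length before treatment begins. If the two events coincide, the set removes no enrolled person. The SAP's added condition of receiving medication would then be redundant, which counts somewhat against this reading. It does have one consequence: the protocol gives 10 as the number enrolled, so signed consents could exceed 10.

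3. *Losses may be few or none.* This stands. Nothing in the documents quantifies them, and delayed withdrawal postpones the first dose without being stated as a ground for exclusion.

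4. *The stakes are modest.* This is an uncontrolled pilot with no decision rule tied to the proportion. The SAP's own secondary-outcome text and the protocol's Specific Aims both call opioid use the primary outcome. This limits the consequence but leaves the wording open.

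A reader might also infer that the result must be 100% by construction, taking study medication to mean BXR alone. The only basis for that is an IRB form field naming one drug, which does not define an analysis set. The section on minimising study medication risks covers both BXR and BSL, and compliance is checked by pill counts, which suit a sublingual product. On this better supported reading, people who start BSL and never reach BXR stay in the denominator as failures.

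**Conclusion.** The concern holds in a limited form and is worth correcting. If the stated set is applied to the induction outcome, the direction is certain: the proportion is overstated or unchanged. The size is unknown and may be zero. In the assumed examples with 10 consented, one loss before dosing adds 5.6 to 10 points (5 to 9 inducted) and two add 12.5 to 20 points (5 to 8 inducted).

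This rests on three assumptions: that the set applies to this outcome, that study medication includes BSL, and that enrolment precedes the first dose. The documents permit all three and settle none.

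A reader might infer that bias is likely, or that the trial's evidence on opioid use is compromised. Neither is supported. Bias is shown to be possible, and the opioid-use outcome that the protocol names as primary is not affected.

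**What to change.** For the induction outcome only, state in SAP C3:

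- **Denominator:** all eligible participants who sign the treatment consent, whatever their number. This should not be fixed at 10, which is the planned number enrolled.
- **Success, for analysis purposes:** receipt of the first BXR injection. Anyone who does not receive it, for any reason, counts as not inducted. This leaves the clinical induction procedure untouched.
- **Reporting:** the proportion with an exact (Clopper-Pearson) 95% CI, and the counts at treatment consent, first BSL dose and first BXR injection.

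Keep the dosed set for the other outcomes, state that study medication there means BSL or BXR, and do not call the set intent-to-treat without qualification; modified intent-to-treat would do.

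The cost is SAP wording only, with no new data. The downside is that the reported induction figure may be less favourable.

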Despite the known effectiveness of buprenorphine sublingual (BSL) maintenance treatment, retention and continued non-prescribed opioid use remain significant limitations. Two recent large trials comparing BSL to other OUD pharmacotherapies found that around 50% or more of patients treated with BSL dropped out of treatment by 3 to 6 months. The first long-acting injectable buprenorphine (Sublocade™) became commercially available in 2018 after receiving an FDA Fast Track and Priority Review designation. This monthly buprenorphine formulation, which is available in two doses (100 mg and 300 mg), can achieve serum buprenorphine concentrations in excess of that achieved by BSL 24 mg per day. Moreover, if an unexpected drug holiday is experienced, at two weeks past the injection due date, μ -opioid receptor remains above 70%, providing some measure of protection against relapse to opioid use. While the Sublocade™ buprenorphine extended-release (BXR) injection product has not yet been compared to BSL treatment for the treatment of OUD, the pharmacologic advantages of BXR can be expected to improve treatment retention and outcome. The extended-release injection aspect should improve compliance and reduce relapse by providing more continuous buprenorphine serum levels as compared to the sublingual formulation. We hypothesize that the BXR injection will have particular benefit for individuals using fentanyl analogues and other HPSO because by providing continuous therapeutic serum buprenorphine levels there will be substantially less opportunity for non-compliance and relapse. Even in the case of a delayed injection, therapeutic levels of buprenorphine will be present for up to two weeks.

We propose an open-label, uncontrolled pilot study, in which patients seeking treatment for OUD who are positive for fentanyl analogues at screening (N = 10) will be inducted onto BSL and then receive BXR injection, with a primary outcome comparison of end of study opioid use compared to baseline. To our knowledge, this would be the first trial to examine the use of this BXR injection formulation for the treatment of OUD patients positive for fentanyl analogues, and the first pharmacotherapy trial of any agent for the treatment of patients with OUD testing positive for HPSO.

Specific Aims and Hypotheses

Specific Aims and Hypotheses

Aim 1: To determine if BXR injection using standard dosing is a feasible treatment for patients with OUD who are positive for HPSO.

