Primary Hypothesis: BXR treatment will be associated with decreased opioid use for OUD patients positive for HPSO. The primary outcome measure will be opioid use during the last two weeks of the study compared to baseline as measured by a combination of urine toxicology and self-report.

Secondary Hypotheses: BXR injection will be associated with reduce symptoms of craving and symptoms of withdrawal as compared to baseline.

If found promising, the results of this pilot trial would support advancement of conducting a controlled trial, with the potential to improve the effectiveness of OUD pharmacotherapy for this subgroup more vulnerable to fatal overdose.

Description of Subject Population

Sample #1

Specify subject population

Adults with OUD testing positive for HPSO

Number of completers required to accomplish study aims

5

Projected number of subjects who will be enrolled to obtain required number of completers

10

Age range of subject population

18-65

Gender, Racial and Ethnic Breakdown

We plan to enroll 10 participants into the study. Both males and females will be recruited. All eligible participants are accepted; however, past experience with recruitment for opioid use disorders suggests that the approximate gender distribution for this study will likely be 20% female and 80% male. Previous and ongoing opiate studies at STARS have had samples comprised of approximately 50% Caucasians, and 50% ethnic minorities distributed as 24% African-American and 22% Hispanic-American, and 4% other. We anticipate a similar representation in this project. We will make every effort to recruit minority patients in order to ensure the generalizability of our findings to the overall treatment population.

Description of subject population

Prospective subjects will be 10 men or non-pregnant women of any ethnicity or race, aged 18-65. Enrolled

subjects will be individuals with OUD who test positive for HPSO.

Recruitment Procedures

Describe settings where recruitment will occur

The project will be completed at the Substance Treatment and Research Services (STARS downtown) situated on [name].

How and by whom will subjects be approached and/or recruited?

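### The protocol and the SAP name different primary outcomes (end-of-study opioid use versus induction onto BXR), and neither says which governs

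*SAP*

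**What the plan says.** **Protocol.** The design paragraph in Background, Significance and Rationale describes an uncontrolled pilot "with a primary outcome comparison of end of study opioid use compared to baseline". Under Specific Aims and Hypotheses, the only aim is feasibility: "To determine if BXR injection using standard dosing is a feasible treatment for patients with OUD who are positive for HPSO". The primary hypothesis under that aim is a fall in opioid use, and the outcome attached to it is again opioid use: "The primary outcome measure will be opioid use during the last two weeks of the study compared to baseline", judged from urine toxicology combined with self-report. No induction proportion appears among the protocol's outcomes.

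**SAP, C3.** Under Hypotheses testing it gives "Primary Outcome: The proportion of participants successfully inducted onto BXR". The next paragraph reads "Secondary Outcomes: BXR treatment will be associated with decreased opioid use for OUD patients positive for HPSO. The primary outcome measure will be opioid use", so one paragraph is headed secondary and calls its content primary. The main analyses use an intent-to-treat set defined as "i.e. on all enrolled patients who receive study medication".

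Neither document contains a precedence statement, an amendment note on this point or a reason for the difference.

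**The concern.** Someone following both documents arrives at two primary outcomes of different kinds. Induction onto BXR asks whether patients can be brought to the injection at all. Opioid use in the last two weeks asks whether they are using less at the end. A participant can receive BXR and still be using opioids in week 12, so one result can look favourable and the other not.

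The study is open-label, so staff see outcomes as they accrue. As far as these two documents go, either outcome could be presented as primary once results are known. The protocol says that promising results would support a controlled trial, so a reader needs to know in advance which result decides whether this pilot was promising.

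If induction is the intended primary outcome, a second problem follows. Success is not defined as an endpoint, and the intent-to-treat wording can be read so that only participants who reached BXR are counted.

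**Working it through.** **1. Is there a figure to reproduce?** No. The sample size of 10 comes with no power, target induction rate or precision for either outcome. The protocol asks for 5 completers from 10 enrolled, and 5 / (1 − 0.5) = 10. But the 50% loss is only implied by those two numbers, so N does not show which outcome the study was planned around.

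**2. The statements side by side.**

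| Place | Opioid use, end of study vs baseline | Proportion inducted onto BXR |
|---|---|---|
| Protocol, Background (design paragraph) | primary | not listed |
| Protocol, Specific Aims and Hypotheses | primary | not listed |
| SAP C3, Primary Outcome | not listed | primary |
| SAP C3, Secondary Outcomes | under the secondary heading, but called primary in the text | not listed |

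**3. Can the order of the documents settle it?** The SAP is dated 2-25-2019. The protocol form is undated in the text available, and its upload list includes a file labelled 2.25.19. Neither text claims to supersede the other, so a rule that the later document governs cannot be applied.

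**4. How far apart are the outcomes in time?** The protocol's Study Procedures place the first BXR injection on study day 4. Taking week 1 to start on study day 1 (an assumption), 12 × 7 = 84 days and the last two weeks are days 71 to 84. The gap is 71 − 4 = 67 days to the start of the window and 84 − 4 = 80 days to its end.

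**5. What does the induction proportion depend on?** Take success to mean receipt of the first BXR injection. This is the natural reading of Study Procedures, although that section uses the word induction for sublingual buprenorphine (BSL): "Study procedures will begin with all participants being inducted onto BSL". For illustration, assume 10 enrolled and 7 reaching BXR; the documents give no expected rate.

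| Denominator | Proportion |
|---|---|
| Intent-to-treat set, study medication = BXR only | 7/7 = 100% |
| Intent-to-treat set, study medication includes BSL, 8 start BSL | 7/8 = 87.5% |
| Same, 9 start BSL | 7/9 = 77.8% |
| Same, 10 start BSL | 7/10 = 70.0% |
| All enrolled | 7/10 = 70.0% |

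The first row does not depend on the 7. With k participants reaching BXR it is k/k = 100% for every k from 1 to 10, so that version of the outcome cannot fail.

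**6. Which reading of study medication do the documents support?** The protocol's section on off-label and investigational drugs counts one drug, Sublocade, which points to BXR only. Its compliance section uses pill counts, which make sense only for BSL, and its section on minimizing study medication risks covers both BXR and BSL. Neither document gives a definition.

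**The case against.** The core conflict is not open to serious dispute, but several points can be made about its weight.

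- **Induction may simply put the feasibility aim into practice.** That is a fair reading of Aim 1. It does not resolve the conflict, because the protocol itself attaches opioid use to that aim as the primary outcome.
- **The stray sentence in the SAP may be a copying slip.** Possibly so. With it deleted, the protocol would still name a different primary outcome from the SAP.
- **The BXR-only reading is strained.** The one-drug answer is a form field, not a definition, and most of the protocol treats BSL as part of the regimen. This stands in part: the two readings are not equally likely. The 100% case shows why a sentence of clarification is needed. It does not predict what the analyst would do.
- **Ongoing review is a data-management phrase.** SAP C2 says collected information "will be easily retrievable, organized, and reviewed on an ongoing basis as well", in a section on data entry. It does not describe an interim look at outcomes and is weak support. The open-label design is enough without it.
- **The rule for combining urine results and self-report is also missing.** True, and it matters if opioid use is chosen, but it is a separate gap.
- **This is a pilot of 10 with both outcomes written down in advance.** That rules out any claim about a confirmatory error rate. It does not excuse leaving the primary outcome unidentified. A trial registration number is given, but the registry entry was not available, so the conclusion is limited to these two documents.

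**Conclusion.** The concern holds and must be fixed. The protocol and the SAP name different primary outcomes, the SAP contradicts itself on the same point, and nothing in either document decides between them. The candidates are a proportion fixed at about day 4 and a change from baseline measured at least 67 days later, and they can disagree. If induction is the intended outcome, the undefined denominator alone moves an illustrative 7 of 10 from 70% to 100%. The day count assumes that week 1 starts on study day 1. The percentages assume that success means the first BXR injection and that 7 of 10 reach it. The labelling conflict itself rests on no assumption. The consequence is uncertainty over what the pilot can be said to have shown.

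**What to change.** Before any outcome data are reviewed, choose one primary outcome, word it identically in both documents and label the other secondary throughout. The choice is the sponsor's.

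- **If induction is primary:** amend the protocol's design paragraph in Background and its Primary Hypothesis paragraph, and reword the sentence in the SAP's secondary outcomes so that it no longer calls opioid use primary.
- **If opioid use is primary:** move it under the SAP's primary outcome heading and list the induction proportion as secondary. The rule for combining urine toxicology and self-report then needs its own text.

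In either case:

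1. Define successful induction onto BXR. Receipt of the first injection is the natural reading, for the sponsor to confirm.
2. State whether study medication in the intent-to-treat definition includes sublingual buprenorphine.
3. State a denominator for the induction proportion that counts participants who fail to reach BXR: all enrolled, or at least all who start sublingual buprenorphine. If study medication is defined to include sublingual buprenorphine, the intent-to-treat set already provides the latter.

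The cost is a few sentences in one amendment to the two documents, with no extra data or visits.
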